## **I- Administrative information:**

### **1. Title:**

Assesment of concentric needle technique for the management of temporomandibular joint internal derangement.

A Randomized control Trial.

### **2. Protocol registration:**

### **3. Protocol version:**

First version.

### **4. Funding:**

Self-funding.

## **II- Introduction:**

### **6. Background and rationale:**

- Research question:**

Is the concentric needles technique a better technique than the traditional two-distant needles technique in TMJ Arthrocentesis?

- Statement of the problem:**

Locating the outflow needle in TMJ arthrocentesis is the challenging step in the two-distant needles technique especially for operators with limited experience which might require multiple insertions increasing the risk of injury to blood vessels and nerves together with patient's discomfort, pain and escape of fluids into the pericapsular tissues.

- Rationale for conducting the research:**

The research population will be divided into two groups. Group A(control group) will be treated by two-distant needles arthrocentesis technique and Group B will be treated by two - concentric needles arthrocentesis technique.

- Review of literature:**

Internal derangement is a common dysfunction of the temporomandibular joint. According to classification of Research Diagnostic Criteria for TMD there are 3 main types of internal TMJ derangement: disc displacement with reduction and disc displacement without reduction with limited mouth opening and disc displacement without reduction without limited mouth opening. The prevalence of disc displacement is about 41% in TMD patients. The most common type is disc displacement with reduction characterized by clicking. Disc displacement with reduction can occur in 33% of asymptomatic individuals.

Arthrocentesis is a simple, safe and minimally invasive technique for the treatment of TMJ disorders. Significant improvements have been reported in terms of reduction in TMJ pain and clicking in the TMJ following arthrocentesis. Most common intra-articular injections in arthrocentesis procedures are steroids, sodium hyaluronate, saline and lactated ringer solution. Arthrocentesis is effective for washing out bradykinin, interleukin-6 and protein.

The technique of two distant needles is done as follows ; Local anaesthetic block of auriculotemporal nerve and infiltration into the areas of joint penetration is done first. Surgical field is draped and painted with Povidone-iodine 5%. External auditory canal is protected from accumulation of blood and fluid using vaselinized gauze. A line was drawn from the lateral canthus of the eye to midpoint of tragus (canthal-tragus line), the first mark was made 1mm in front of the tragus and 2mm below the line representing the posterior extent of glenoid fossa, and the second mark was made 20 mm anterior to midtragal point and 10 mm below canthal-tragus line representing the height of articular eminence. A 20

gauge needle is then inserted into the upper joint space at the glenoid fossa and 2ml of Ringer's solution are injected to distend the upper joint space. A second 20 gauge needle is inserted in the area of the articular eminence to establish a free flow of the irrigating solution through the upper joint space. Then, the joint is irrigated with 100-300 mL of Ringer's solution.

The technique of concentric needle is done as follows; a 27-gauge, 50- mm-long needle is inserted into a 21-gauge, 38-mm needle. The longer 27-gauge needle does not block the end of the larger needle hub from which the solution outflows. In this way, joint irrigation is performed through the inner needle with the solution outflow through the outer needle hub. Irrigation through this concentric-device combination allows single puncture of the TMJ with a single needle. A horizontal line is drawn from the corner of the eye to the tragus and a puncture mark is made 10 mm from the tragus and 0.5 mm below this line. The concentric-needle unit is inserted into the upper joint space while the patient is asked to open the mouth halfway to allow entry of the needle. Once it is inside the joint space, lavage is performed with lactated Ringer solution. The advantages of the single-needle method include the use of a single puncture for both irrigation and outflow, hence achievement of efficient arthrocentesis without the need for a second needle, decreasing the risk of losing the correct place during inserting the needle. This also leads to less patient discomfort, a lesser risk of infection, and less bleeding. Another advantage of a single puncture technique is that it reduces patient pain in the postoperative period so this reduces the need for extra care postoperatively. The amount of local anesthesia is much less for a single puncture than that needed for a double-puncture or arthrocentesis, thus reducing the complications due to local anesthetics. A single-needle technique reduces the risk of facial nerve injury, because an anteriorly positioned second needle can traumatize the facial nerve, which lays anteriorly and medially to the glenoid fossa, just where the second needle is inserted.

## **7. Objective of the study:**

### **- Aim of the study:**

The aim of the study is to evaluate the effectiveness of using two concentric needles in comparison with the normal traditional two distant needles.

## **8. Trial design:**

Randomized control trial.

### **III- Methodology:**

#### **A) Participants, intervention and outcomes**

##### **9. Study setting:**

Patients will be selected from the outpatient clinic of the Oral and Maxillofacial Surgery Department, Faculty of Dentistry, Cairo University.

##### **10. Eligibility criteria:**

###### **a. Inclusion criteria:**

- 1- Patients with age ranges from 18-60.
- 2- Patients with painful clicking.
- 3- Patients free of systemic conditions that might affect the TMJ or interfere with carrying out the surgical procedure (osteoarthritis, rheumatoid arthritis, uncontrolled diabetes).

###### **b. Exclusion criteria:**

- 1- Patients out of the specified range group
- 2- Patients with painless TMJ clicking.
- 3- Patients with osteo-arthritic changes of the TMJ.
- 4- Patients with systemic conditions that might affect the TMJ or interfere with carrying out the surgical procedure (osteoarthritis, rheumatoid arthritis, uncontrolled diabetes).
- 5- Patients with previous TMJ surgeries.

##### **11. Group Allocation**

Patients will be randomly allocated to one of the two groups using computer randomization.

##### **12. Interventions:**

###### **○ Diagnostic procedure:**

- a) Patient questionnaire: a questionnaire will be recorded by the examiner including: Chief complaint, Personal data, medical history.
- b) Consent: Informed consent will be obtained from patients regarding the surgical procedure and inclusion in the study.
- c) Clinical examination: oro facial examination with specific emphasis on the TMJ regarding pain, clicking, maximum inter-incisal mouth opening and lateral excursions.

###### **○ operative procedures:**

TMJ arthrocentesis will be performed under local anesthesia.

- External auditory canal is protected from accumulation of blood and fluid using vaselinized gauze.

- The surgical field will be scrubbed and draped in a standard sterile fashion.

#### A-The standard two – distant needles technique:

Local anaesthetic block of auriculotemporal nerve and infiltration into the areas of joint penetration is done first. Surgical field is draped and painted with Povidone-iodine 5%. External auditory canal is protected from accumulation of blood and fluid using vaselinized gauze. A line was drawn from the lateral canthus of the eye to midpoint of tragus (canthal-tragus line), the first mark was made 1 mm in front of the tragus and 2mm below the line representing the posterior extent of glenoid fossa, and the second mark was made 20 mm anterior to midtragal point and 10 mm below canthal-tragus line representing the height of articular eminence. A 20 gauge needle is then inserted into the upper joint space at the glenoid fossa and 2ml of Ringer's solution are injected to distend the upper joint space. A second 20 gauge needle is inserted in the area of the articular eminence to establish a free flow of the irrigating solution through the upper joint space. Then, the joint is irrigated with 100-300 mL of Ringer's solution.

#### B-The concentric-needle cannula technique:

The technique of concentric needle is done as follows; a 27-gauge, 50- mm-long needle is inserted into a 21-gauge, 38-mm needle. The longer 27-gauge needle does not block the end of the larger needle hub from which the solution outflows. In this way, joint irrigation is performed through the inner needle with the solution outflow through the outer needle hub. Irrigation through this concentric-device combination allows single puncture of the TMJ with a single needle. Local anaesthetic block of auriculotemporal nerve and infiltration into the areas of joint penetration is done first. Surgical field is draped and painted with Povidone-iodine 5%. External auditory canal is protected from accumulation of blood and fluid using vaselinized gauze. A horizontal line is drawn from the corner of the eye to the tragus and a puncture mark is made 10 mm from the tragus and 0.5 mm below this line. The concentric-needle unit is inserted into the upper joint space while the patient is asked to open the mouth halfway to allow entry of the needle. Once it is inside the joint space, lavage is performed with lactated Ringer solution.

- Post-operative care:

Patients will be prescribed Augmentin 1gm 2 hours before procedure and 24 hours after procedure as a prophylaxis. Brufen 600 mg will be taken after the procedure. The patient will be instructed to take Alphintern 2 tablets before food 3 times daily.

### **13. Outcomes:**

Prioritization of outcome	Outcome	Method of measurement	Unit of measurement
Primary outcome	pain	Visual analogue scale	Score
Secondary outcome	complications	Edema, Nerves and arteries injuries	Inspection and Palpation

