**14. Participant timeline:**

	Study Period		
	Enrollment	Allocation	Post-allocation
Time Point	-t 1	0	t 1
Enrolment:			
Eligibility Screen Informed Consent			
Pt. preparation			
Interventions:			
Surgical procedure			
Assessments			
Assessment of pain,outflow rate and complications			1 day post- operative

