**B) Data collection, management and analysis:**

**17. Data collection methods:**

Data will be collected by AAHM,DRAK,MAEF,AES

Telephone numbers of all patients included the study will be recorded as a part of the written consent

All patients will be given a phone call at the time of the pre-determined follow up dates

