**21. Harms:**

-Pain.

-Swelling and edema.

-Nerves injury: Zygomatic, Temporal and Auricotemporal nerves

-Arteries injury.

To avoid injury to nerves and arteries: sticking to proper anatomical landmarks

In case of nerve injuries: Stop the insertion of the needle and redirect it

In case of arteries injuries: -Apply pressure by gauze

-Use cold packs and antibiotic in case of hematoma

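### Inspection and palpation, the only stated method for nerve injury, cannot show sensory loss from the auriculotemporal nerve, so the harms count in the only secondary outcome would be incomplete.

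*Protocol*

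**What the plan says.** The outcome table in section 13 has pain as the primary outcome and complications as the only secondary outcome. The complications are "Edema, Nerves and arteries injuries", and the accompanying entry is "Inspection and Palpation". The cells look misplaced: the list of complications stands in the method column and the examination technique in the unit column. No other technique for finding complications appears anywhere in the protocol.

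Section 21 lists "Nerves injury: Zygomatic, Temporal and Auricotemporal nerves". The operative description in section 12 states for the two-needle arm "Local anaesthetic block of auriculotemporal nerve and infiltration into the areas of joint penetration is done first", and the concentric arm has the same step.

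The timeline in section 14 places "Assessment of pain,outflow rate and complications" at one day after the operation, as a single time point. Section 17 says "All patients will be given a phone call at the time of the pre-determined follow up dates".

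Before the procedure, section 12 provides an "oro facial examination with specific emphasis on the TMJ regarding pain, clicking, maximum inter-incisal mouth opening and lateral excursions". The questionnaire in Appendix B asks about trismus, joint noises, pain, locking, earlier facial injury and medication. Neither names sensation or facial movement.

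**The concern.** The method fixed in the outcome table does not fit one of the injuries the protocol lists. A sensory deficit has to be asked about or tested, and the protocol provides for neither. For the motor branches, inspection works only if the face is put in motion, and the text does not say that it will be. Without a recorded baseline, a deficit found on day 1 cannot be separated from one that was already there. That possibility is realistic, since Appendix B itself asks about past facial injury.

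Nerve injury is part of the case for the trial. Section 6 describes repeated insertions as "increasing the risk of injury to blood vessels and nerves", and its literature review adds that an anterior second needle may damage the facial nerve. A count of complications that leaves out sensory injuries by construction could be read as evidence of safety when those injuries were never looked for.

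**Working it through.** **The plan's own figure.** The one calculated number is the sample size, and this point does not affect it. From section 19: means 4.100 and 6.600, SDs 2.183 and 1.430, alpha 0.05, power 0.80, ratio 1. Common SD = √((2.183² + 1.430²)/2) = 1.845. Standardised difference = 2.5/1.845 = 1.355. A two-sided t-test needs 9.61, so 10 per arm and 20 in all, with power 0.817. The stated 20 is reproduced.

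**Injury listed against method given.**

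| Injury (sections 13 and 21) | Shown by inspection and palpation? | Pre-operative record named? |
|---|---|---|
| Edema, hematoma | Yes | Not needed in the same way |
| Zygomatic and temporal nerves (facial weakness) | Yes, if the patient is asked to move; not stated | No |
| Auriculotemporal nerve (sensory loss) | No | No |

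The protocol blocks the auriculotemporal nerve to anaesthetise the area, so by its own account this nerve carries sensation.

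**Mode of assessment.** Inspection and palpation need the patient to be present. Section 14 puts the assessment on day 1, and section 17 describes contact at follow-up dates as a telephone call. As written, these do not fit together, and the conflict affects edema and hematoma as well as nerve injury.

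**Size.** The protocol gives neither a nerve-injury rate nor a detection probability, so the under-count cannot be derived. The following uses assumed values only. With true rate p, detection probability s and 10 patients in an arm, the chance of recording at least one case is 1 − (1 − p·s)^10.

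| Assumed p | s = 1 | s = 0.5 | s = 0 |
|---|---|---|---|
| 0.10 | 1 − 0.90^10 = 65% | 1 − 0.95^10 = 40% | 0% |
| 0.20 | 1 − 0.80^10 = 89% | 1 − 0.90^10 = 65% | 0% |

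The last column applies only to purely sensory injuries that no patient mentions.

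**What detection does for the comparison.** Assume true rates of 30% and 10%. Normal approximation, with the pooled standard error under the null:

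- Full detection: difference 0.20; null SE √(2 × 0.20 × 0.80/10) = 0.179; alternative SE √((0.21 + 0.09)/10) = 0.173; z = (0.20 − 1.96 × 0.179)/0.173 = −0.87; power about 19%.
- Half detected in both arms (15% and 5%): difference 0.10; null SE √(2 × 0.10 × 0.90/10) = 0.134; alternative SE √((0.1275 + 0.0475)/10) = 0.132; z = (0.10 − 1.96 × 0.134)/0.132 = −1.23; power about 11%.

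A two-sided Fisher test with 10 per arm gives p = 2 × C(10,4)/C(20,4) = 420/4845 = 0.087 for 4 against 0, and 2 × C(10,5)/C(20,5) = 504/15504 = 0.033 for 5 against 0. The comparison is weak even with perfect ascertainment.

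**The case against.** The strongest reply is that the nerve expected to differ between arms is a motor nerve. The literature review in section 6 ties the advantage of a single puncture to the facial nerve. Facial weakness can be seen, and asking a patient to raise the brow is an ordinary part of inspection that section 13 does not exclude. No part of the protocol predicts a difference in the auriculotemporal nerve, which is blocked in both arms. This stands. A reader might infer that the method would record few or no nerve injuries of any kind, or that it would hide the difference the trial is looking for. The protocol supports neither inference.

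A reader might also take the 65% and 89% above as the chance that real injuries end up recorded as none out of ten. That holds only if every injury is purely sensory, none is detected and no patient reports numbness. Three nerves are listed, and section 29 promises follow-up until healing, which gives numbness a further chance to surface, though outside the outcome time point.

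Two further replies carry some weight. The examination in section 12 emphasises the joint without ruling out other checks, so the accurate statement is that no nerve baseline is named, not that none could be taken. And a terse entry in the wrong column is limited evidence that other bedside checks are excluded.

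None of this supplies a sensory test or a question on numbness. Nor can an analysis plan repair the gap, because signs that were never examined cannot be recovered in analysis.

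**Conclusion.** The point holds for the auriculotemporal nerve. The stated method cannot show its sensory loss, so such injuries would be under-counted in the only secondary outcome. For the zygomatic and temporal branches the narrower statement is that a movement test is not specified. In both cases no pre-operative nerve status is named.

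The direction follows from the method, but the amount cannot be stated from the protocol; the rates used above are assumptions. With 10 per arm, the consequence lies in how far the harms description can be trusted. Better ascertainment would make the counts valid but would not enable this trial to demonstrate a difference in rare events. The primary outcome and the sample size are untouched. The change should be made because it is cheap and the outcome is not validly measured as written, but it does not put the trial's main conclusion at risk.

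**What to change.** In section 13, put the method and the unit in their proper columns. Keep inspection and palpation for edema and hematoma. Define nerve injury as a new deficit, compared with a pre-operative check, on:

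- brow raise and eye closure;
- light touch in the preauricular and temporal skin, compared with the other side;
- a direct question about numbness.

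Record yes or no for each nerve before the procedure and on day 1, and add the pre-operative check to the examination in section 12. Reconcile sections 13 and 14 with the phone call in section 17 so that the day-1 complication assessment is in person, as inspection and palpation already require.

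The cost is one to two minutes per examination and a few case-report fields, with no equipment. If day 1 is at present only a call, a visit is needed, but the method now written would need one too. Minor transient deficits will be counted. Light touch is subjective and the protocol states no assessor blinding, so an examiner who knows the arm could influence the result; this should be acknowledged when the counts are reported.

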**14. Participant timeline:**

	Study Period		
	Enrollment	Allocation	Post-allocation
Time Point	-t 1	0	t 1
Enrolment:			
Eligibility Screen Informed Consent			
Pt. preparation			
Interventions:			
Surgical procedure			
Assessments			
Assessment of pain,outflow rate and complications			1 day post- operative

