### **29. Post-trial care**

All patients will be followed up until complete healing and satisfactory results occur.

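### The only scheduled check for complications is on day 1, so insertion injuries that resolve before then have no stated route into the secondary outcome

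*Protocol*

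**What the plan says.** The participant timeline (Protocol, section 14) has three columns: enrolment, allocation and one post-allocation time point. Its single assessment row reads "Assessment of pain,outflow rate and complications", and the only entry is "1 day post- operative".

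The outcomes table (section 13) names complications as the secondary outcome and lists "Edema, Nerves and arteries injuries", with inspection and palpation as the means of finding them. It gives no time or window.

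The statement of the problem (section 6) says that the search for the outflow needle may need "multiple insertions increasing the risk of injury to blood vessels and nerves", and adds "patient's discomfort, pain and escape of fluids into the pericapsular tissues". The harms section (section 21) says of nerve injury: "Stop the insertion of the needle and redirect it". For arterial injury it describes gauze pressure, with further measures if a hematoma forms. It does not say that such events are recorded as outcome data.

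Two other places mention later contact. Section 17 promises telephone calls on several pre-set follow-up dates, which are not given. Section 29 states: "All patients will be followed up until complete healing and satisfactory results occur". Neither is linked to the secondary outcome.

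**The concern.** The new technique is proposed partly because a single puncture should cause fewer insertion injuries. Those injuries occur while the needle is being placed, but the protocol schedules its one look for complications on the following day. A bleed that stopped under pressure, or a nerve contact relieved when the needle was redirected, may leave nothing to see or feel by then.

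The secondary outcome could therefore miss some of the events on which the two techniques are expected to differ. If such events are more frequent with two needles, as section 6 supposes, more of them would be lost from that arm and the observed contrast would shrink. An intra-operative event that nobody wrote down cannot be reliably recovered later, so the matter has to be settled before enrolment.

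**Working it through.** **1. The plan's own figure.** The only calculation in the protocol is the sample size in section 19, which rests on day-1 pain: means 4.100 and 6.600, SDs 2.183 and 1.430, alpha 0.05, power 0.80, ratio 1.

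- Difference: 6.600 − 4.100 = 2.5.
- Pooled SD: √((2.183² + 1.430²)/2) = √((4.765 + 2.045)/2) = 1.845.
- Two-sided t-test: 10 per arm gives power 0.817, hence 20 in total. The normal approximation gives 9 per arm.

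The stated 20 is reproduced. It does not depend on complications, so changing when they are recorded leaves it as it is.

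**2. When the listed events arise and when they are looked for.**

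| Event | When the protocol places it | Scheduled look | Route into the outcome |
|---|---|---|---|
| Edema | Not stated (sections 13, 21) | Day 1 | Yes, if present on day 1 |
| Nerve injury | During insertion (sections 6, 21) | Day 1 | Yes, if still evident; otherwise none stated |
| Artery injury | During insertion (section 6); pressure or hematoma care (section 21) | Day 1 | Yes, if still evident; otherwise none stated |
| Any listed event first noticed after day 1 | Not addressed | None scheduled | None stated |

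**3. Size.** Let p_C and p_T be the true proportions of control and concentric-needle patients with an insertion-related event, and let f be the share of these events no longer evident on day 1, taken as equal in both arms. The day-1 assessment then estimates

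(1 − f) × (p_C − p_T).

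None of the three quantities is in the documents. As an assumed illustration only, take p_C = 4/10 and p_T = 1/10:

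- f = 0: difference 30 percentage points.
- f = 0.5: 0.20 − 0.05 = 15 percentage points.
- f = 1: 0 percentage points.

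The range runs from no loss to complete loss. The direction is clear, but the amount is not.

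**4. What 10 per arm could show in any case.** With full capture of 4/10 against 1/10, Fisher's exact test has an upper tail of

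[C(10,4)·C(10,1) + C(10,5)·C(10,0)] / C(20,5) = (2100 + 252)/15504 = 0.152,

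and so a two-sided p of about 0.30.

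**The case against.** The strongest reply is that day 1 is when the assessment is made, and not a rule about which events count. Section 13 sets no window, so an assessor on day 1 could note a bleed from the day before. The same row also holds outflow rate, which can only be observed during lavage, so its timing is evidently loose. Most other cells of the timeline are blank in the text available, even the one for the surgical procedure, so marks may have been lost in extraction.

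Much of this stands. A reader might infer that all intra-operative events are excluded from the secondary outcome. The documents do not support that: nerve and artery injuries are named components, and any still evident on day 1 is counted. What remains is that detection rests on inspection and palpation on day 1, and no section asks the operator to record an event as it happens. The misplaced outflow rate is itself a reason to clarify the row.

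A reader might also infer that the trial would report no difference in complications because of when it looked. That does not follow. Even the assumed 4/10 against 1/10, fully captured, gives p of about 0.30, so the small sample limits this comparison whatever the timing. Likewise, zero events in 10 patients is compatible with a true rate up to 1 − 0.05^(1/10) = 26% (one-sided 95%), but that holds for any zero count and says nothing about timing.

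Finally, section 6 claims "less patient discomfort, a lesser risk of infection, and less bleeding" for the single puncture, and it is tempting to say that the day-1 look misses infection and fluid escape. They go uncounted because section 13 does not list them, which is a matter of outcome definition and not of timing.

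**Conclusion.** The point holds in limited form. Day 1 is the only scheduled assessment of complications, while the injuries in the problem statement arise during needle insertion and are managed then. Injuries that resolve before day 1 have no stated route into the secondary outcome, and insertion-related events could be under-counted. The size cannot be derived from the documents. The under-count would favour neither conclusion about pain and does not touch the primary outcome or the sample size.

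This rests on two assumptions: that the day-1 entry is the only one in the assessment row, and that some insertion injuries leave no sign the next day. The second is plausible from section 21, but the protocol does not quantify it.

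The follow-up wording is also inconsistent. Section 14 has one time point, section 17 speaks of several dates, and section 29 has an open-ended period. The protocol does not say whether anything learned at the later contacts counts.

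**What to change.** 1. In sections 13 and 14, define the complication outcome as any listed event (edema, nerve injury or artery injury) from first needle insertion through day 1.
2. Record these events on the operative record and again at the day-1 assessment. Because the operator knows which technique is used, word the intra-operative items as observable events and not as judgements.
3. Report intra-operative and day-1 events separately by arm.
4. Move outflow rate to the procedure time point in section 14.
5. Reconcile the single time point in section 14 with the several follow-up dates in section 17 and the follow-up in section 29. At contacts already planned, note any later event that a patient reports, such as a persisting nerve deficit, and describe it outside the formal outcome. Telephone calls cannot supply inspection or palpation, so they cannot extend the outcome as section 13 measures it.

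The cost is about one line on the operative record, slightly more data entry, and higher complication counts in both arms. No new visit is needed, and the sample size stays at 20.
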